#### 4.3 Exclusion Criteria

1. Prior treatment with cabozantinib
2. Receipt of any type of small molecule kinase inhibitor (including investigational kinase inhibitor) within 2 weeks before first dose of study treatment.
3. Receipt of any type of cytotoxic, biologic or other systemic anticancer therapy (including investigational) except agents to maintain castrate status within 4 weeks before first dose of study treatment. Antiresorptive bone agents are also allowed.
4. Subject has received abiraterone acetate or enzalutamide within 2 weeks before enrollment.
5. Radiation therapy for bone metastasis within 2 weeks, any other radiation therapy within 4 weeks before first dose of study treatment. Systemic treatment with radionuclides within 6 weeks before the first dose of study treatment. Subjects with clinically relevant ongoing complications from prior radiation therapy are not eligible.
6. Known brain metastases or cranial epidural disease unless adequately treated with radiotherapy and/or surgery (including radiosurgery) and stable for at least 4 weeks prior to first dose of study treatment after radiotherapy or at least 4 weeks prior to first dose of study treatment after major surgery (*e.g.*, removal or biopsy of brain metastasis). Subjects must have complete wound healing from major surgery or minor surgery before first dose of study treatment. Eligible subjects must be neurologically asymptomatic and without corticosteroid treatment for neurological indications at the time of first dose of study treatment.
7. Concomitant anticoagulation with coumarin agents (*e.g.*, warfarin), direct thrombin inhibitors (*e.g.*, dabigatran), direct factor Xa inhibitor betrixaban, or platelet inhibitors (*e.g.*, clopidogrel). Allowed anticoagulants are the following:
  - a. Prophylactic use of low-dose aspirin for cardio-protection (per local applicable guidelines) and low-dose low molecular weight heparins (LMWH).
  - b. Therapeutic doses of LMWH or anticoagulation with direct factor Xa inhibitors rivaroxaban, edoxaban, or apixaban in subjects without known brain metastases who are on a stable dose of the anticoagulant for at least 1 week before first dose of study treatment without clinically significant hemorrhagic complications from the anticoagulation regimen or the tumor.
8. The subject has prothrombin time (PT)/INR or partial thromboplastin time (PTT) test  $\geq 1.3 \times$  the laboratory ULN **within 14 days before the first dose of study treatment**.
9. The subject has uncontrolled, significant intercurrent or recent illness including, but not limited to, the following conditions:
  - a. Cardiovascular disorders:
    - i. Congestive heart failure New York Heart Association Class 3 or 4, unstable angina pectoris, serious cardiac arrhythmias.
    - ii. Uncontrolled hypertension defined as sustained blood pressure (BP)  $>140$  mm Hg systolic or  $>90$  mm Hg diastolic despite optimal antihypertensive treatment.
    - iii. Stroke (including transient ischemic attack [TIA]), myocardial infarction (MI), or other ischemic event, or thromboembolic event (*e.g.* deep venous thrombosis, pulmonary embolism) within 6 months before first dose.
  - b. Gastrointestinal (GI) disorders including those associated with a high risk of

perforation or fistula formation:

- i. The subject has evidence of tumor invading the GI tract, active peptic ulcer disease, inflammatory bowel disease (*e.g.*, Crohn's disease), diverticulitis, cholecystitis, symptomatic cholangitis or appendicitis, acute pancreatitis, acute obstruction of the pancreatic duct or common bile duct, or gastric outlet obstruction.
  - ii. Abdominal fistula, GI perforation, bowel obstruction, or intra-abdominal abscess within 6 months before first dose.  
**Note: Complete healing of an intra-abdominal abscess must be confirmed before first dose.**
  - c. Clinically significant hematuria, hematemesis, or hemoptysis of > 0.5 teaspoon (2.5mL) of red blood, or other history of significant bleeding (*e.g.*, pulmonary hemorrhage) within 12 weeks before first dose.
  - d. Cavitating pulmonary lesion(s) or known endotracheal or endobronchial disease manifestation.
  - e. Lesions invading or encasing any major blood vessels. Subjects with lesions invading the intrahepatic vasculature, including portal vein, hepatic vein, and hepatic artery, are eligible.
  - f. Other clinically significant disorders that would preclude safe study participation.
    - i. Serious non-healing wound/ulcer/bone fracture.
    - ii. Uncompensated/symptomatic hypothyroidism.
    - iii. Moderate to severe hepatic impairment (Child-Pugh B or C).
10. Major surgery (*e.g.*, GI surgery, removal or biopsy of brain metastasis) within 8 weeks before first dose of study treatment. Complete wound healing from major surgery must have occurred 1 month before first dose and from minor surgery (*e.g.* simple excision, tooth extraction) at least 10 days before first dose. Subjects with clinically relevant ongoing complications from prior surgery are not eligible.
11. Corrected QT interval calculated by the Fridericia formula (QTcF) > 500 ms per electrocardiogram (ECG) within 28 days before first dose of study treatment [add reference for Fridericia formula].  
**Note: If a single ECG shows a QTcF with an absolute value > 500 ms, two additional ECGs at intervals of approximately 3 min must be performed within 30 min after the initial ECG, and the average of these three consecutive results for QTcF will be used to determine eligibility.**
12. Inability to swallow tablets.
13. Previously identified allergy or hypersensitivity to components of the study treatment formulations.
14. Diagnosis of another malignancy within 2 years before first dose of study treatment, except for superficial skin cancers, or localized, low-grade tumors deemed cured and not treated with systemic therapy.

#### 4.4 Molecular Eligibility

To be eligible, a patient's tumor must have evidence of gene amplification, an activating mutation, or overexpression of one of the following genes: MET, KIT, RET, VEGFR-1, VEGFR-2, VEGFR-3, FLT3, AXL, TRKB, or TIE2. In the event of activating mutations, the observed mutation must be of Level 1, Level 2, or Level 3 as annotated by OncoKB ([www.oncokb.org](http://www.oncokb.org)). Eligibility can be met by **at least one** of the following diagnostic tests:

- 1) DNA sequencing of a metastatic tumor biopsy specimen showing gene amplification or activating mutation using a CLIA-certified assay. Tumor tissue samples must have been collected within 6 months of enrollment.
- 2) Protein overexpression in a metastatic tumor biopsy specimen determined by immunohistochemistry (IHC) showing 3+ protein expression using a CLIA-certified assay. These

- include common in-house KIT and commercial reference labs for panTRK (*e.g.* NeoGenomics) and cMET (*e.g.* NeoGenomics, Caris, Mayo Clinic).
- 3) CLIA-certified commercial cell free DNA assay (either Guardant360 or FoundationOneLiquid assay) reporting gene amplification or activating mutation *within 6 months of enrollment*.
    - a. For the Guardant360 Liquid Biopsy amplification must be at least (++) or (+++) for to meet eligibility.
    - b. For the FoundationOneLiquid assay, amplification will be eligible. Reports that have an “equivocal” or “subclonal” designation will not be eligible.
  - 4) Any non-CLIA certified assay such as RNA expression profiling of a metastatic tumor biopsy specimen showing overexpression must be confirmed by a CLIA-certified assay (*i.e.*, immunohistochemistry showing 3+ protein expression)

Patients who do not meet molecular eligibility criteria will be allowed to enroll if they have liver metastases that meet RECIST criteria for measurable disease. Patients with prostate adenocarcinoma or NEPC will be allowed to enroll.

#### 4.5 Lifestyle Considerations

As food increases exposure levels of cabozantinib, subjects should fast (with the exception of water) for at least 2 h before taking their dose of cabozantinib. After the 2-hour fast, subjects are to take cabozantinib with a full glass of water (minimum of 8 oz or 240 mL) with no more food intake for one-hour post-dose.

#### 4.6 Screen Failures

Screen failures are defined as participants who consent to participate in the clinical trial but are not subsequently randomly assigned to the study intervention or entered in the study. A minimal set of screen failure information is required to ensure transparent reporting of screen failure participants, to meet the Consolidated Standards of Reporting Trials (CONSORT) publishing requirements and to respond to queries from regulatory authorities. Minimal information includes demography, screen failure details, eligibility criteria, and any serious adverse event (SAE).

Individuals who do not meet the criteria for participation in this trial (screen failure) because of not having a molecular abnormality may be rescreened. Rescreened participants should be assigned the same participant number as for the initial screening.

#### 4.7 Strategies for Recruitment and Retention

The study will be performed in the Prostate Cancer Clinical Trials Consortium, which consists of over 40 academic and affiliated sites across the U.S. Approximately eight PCCTC sites will participate in the trial. Patients diagnosed with documented progressive metastatic CRPC disease who are visiting Oncology Clinics of participating institutions or other for their standard of care visit will be approached for recruitment for this study. Investigators or delegates under their direct supervision may perform pre-screening of these potential subjects.

Recognizing that many centers (both in and out of the PCCTC in the NYC area) perform genomic sequencing as standard of care in men with CRPC, we will inform PCCTC members and other colleagues about this molecular selected trial to encourage referrals for this study. This will be done via email and at PCCTC meetings (at GU ASCO, ASCO Annual Meeting and PCF Annual Retreat). We will also submit a “clinical trials in progress” poster for presentation at ASCO Annual Meeting.

## **5 REGISTRATION PROCEDURES**

### **5.1 Subject Registration (WCM only)**

Subjects will be registered within the WRG-CT as per the standard operating procedure for Subject Registration.

### **5.2 Subject Registration (Sub-Sites)**

Subjects will be centrally registered Monday through Friday from 9:00am to 4:00pm with the Weill Cornell Medicine Joint Clinical Trials Office (JCTO). To register a new study subject, email the following documents to [[contact]](mailto:[contact]):

- Completed WCM subject registration form
- First and last page of the fully executed informed consent form, plus additional pages if checkboxes for correlative studies are required
- Fully executed HIPAA research authorization form
- Eligibility checklist signed and dated by investigator and research nurse
- Documentation of any eligibility waivers granted
- Redacted source documentation to verify eligibility

Note that attachments larger than 4.5 MB are not accepted, so larger attachments should be split into more than one email. Central registration information is reviewed and entered into REDCap Cloud.

## 6 STUDY PROCEDURES

### 6.1 Schedule of Assessments

The study flow chart, including all procedures to be performed during the study, is presented below. Prior to engaging in any study procedure, each patient must sign and date an informed consent form. The following schedule of assessments applies to all subjects; assessments that are more frequent should be obtained if clinically indicated. Cycles are scheduled to be 28 days in length.

If the subject is unable to have a study assessment taken within the defined time window due to an event outside of his or her control (e.g., clinic closure, personal emergency, inclement weather, vacation), the assessment should be performed as close as possible to the required schedule.

Cycle = 28 days	Screening	Cycle 1			Cycle 2	Cycle 3	Cycle 4 +	End of Treatment	Survival Follow-Up
	Day -30 to -1	Day 1	Day 14	Day 21 (+ 3 days)	Day 1 (± 3 days)	Day 1 (± 3 days)	Day 1 (± 3 days)	Post-Treatment	
Informed consent	X								
Medical History 	X								
Physical Exam 	X	X			X	X	X	X	
Vital Signs	X	X	X		X	X	X	X	
Demographics	X								
ECOG Performance Status	X	X			X	X	X	X	
ECG	X								
CBC w. differential and platelet count	X	X			X	X	X	X	
Complete Metabolic Panel 	X	X			X	X	X		
LDH	X	X					X 		
Lipase	X	X 					X 		

 Including cancer history, prior therapy including prior radiotherapy, surgical/pathological reports,

 Including height at baseline and weight at each subsequent visit

 Also include direct bilirubin with known Gilbert's syndrome

	Screening	Cycle 1			Cycle 2	Cycle 3	Cycle 4 +	End of Treatment	Survival Follow-Up
	Day -30 to -1	Day 1	Day 14	Day 21 (+ 3 days)	Day 1 (± 3 days)	Day 1 (± 3 days)	Day 1 (± 3 days)	Post-Treatment	
Cycle = 28 days									
UA and UPCR (24-hr urine, if indicated)	X						X 		
PT/INR and PTT	X								
Thyroid function tests (TSH/FT4 initially. If normal, then TSH thereafter)	X						X 	X	
Testosterone	X						X 	X	
Circulating Immune Activity Sample	X	X 					X 	X	
cfDNA 	X	X 					X 	X	
Tumor assessment (CT/MRI a/p, CT chest bone scan)	X						X 	X 	
PSA sample	X	X					X 	X	
Pre-treatment biopsy 	X								
On-treatment biopsy 				X					
Skeletal-related events 	X	X			X	X	X	X	

 cfDNA, circulating immune activity, lipase can be collected within 30 days prior to C1D1 or pre-dose C1D1

 When plasma DNA is collected, it should be collected as close to biopsy date as possible, including same day. In the event it is collected on the same day, the specimen should be acquired *prior* to the biopsy procedure.

 Every 12 weeks (± 5 days) until disease progression. For EOT, does not have to be repeated if done within 6 weeks of visit.

 Assess continuously until disease progression

 Every 12 weeks beginning with C4D1 (e.g. C4, C7, C10, etc).

 Collect only on C4D1

 Pre-treatment biopsy can be waived provided that adequate archival material for molecular analyses available from biopsy performed within 3 months of enrollment

 On-treatment biopsy during cycle 1 after 3 weeks of therapy. Biopsy must be performed between day 21 and day 24 on therapy (inclusive). *NB: cabozantinib must be held 5 days before and 5 days after biopsy*

Cycle = 28 days	Screening	Cycle 1			Cycle 2	Cycle 3	Cycle 4 +	End of Treatment	Survival Follow-Up
	Day -30 to -1	Day 1	Day 14	Day 21 (+ 3 days)	Day 1 (± 3 days)	Day 1 (± 3 days)	Day 1 (± 3 days)	Post-Treatment	
Concomitant medications 	X	X			X	X	X	X	
Adverse events 	X	X	X		X	X	X	X	
Health Care Resources 	X	X			X	X	X	X	
Cabozantinib dosing 		X			X	X	X		
Dispense/return of oral study drug and compliance accounting		X			X	X	X	X	
Additional cancer treatment, survival status								X	Subjects will be followed every 12 weeks for 2 years after completion of the study or until death, whichever occurs first

 Document those taken from 30 days prior to treatment through 30 days after the decision to discontinue study treatment

 Document new or worsening events from time of informed consent through 30 days after the last dose of study treatment (related SAEs at any time). Adverse events information will be collected at study visits and may also be collected at any time over the phone or by spontaneous subject report. At study visits where any study treatment is administered, adverse events will be documented pre- and post-dose. Certain AEs and all SAEs that are ongoing 30 days after last dose of study treatment are to be followed until resolution or determination by the investigator that the event is table or irreversible.

 Collection of hospital admissions, length of stay, and relevant procedures.

 Cabozantinib taken once daily at home

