## 6.2 Screening Visit

### (Day -30 to -1 days before start of treatment)

- Informed Consent
- Demographics
- Medical History
  - Previous therapy
  - Surgical report will include date and type of surgery +/- lymphadenectomy
  - Medication history
  - Radiotherapy report will include modality of therapy with prescribed dose and field and dates of therapy
- Previous systemic (hormonal, chemo, other) therapy – drugs, doses, dates of therapy
- Complete Physical Exam including height and weight
- Vital Signs
- ECOG Performance Status
- CBC with differential and platelet count
- CMP (with direct bilirubin with known Gilbert's syndrome)
- PSA
- Testosterone
- Thyroid function tests (TSH/FT4)
- PT/INR and PTT
- UA and UPCR
- EKG
- Circulating Immune Activity sample (may be collected at screening or pre-dose C1D1)
- cfDNA (may be collected at screening or pre-dose C1D1)
- CT or MRI abdomen/pelvis
- CT chest
- Bone scan
- A biopsy of at least one metastatic site or primary prostate prior to beginning therapy. However, adequate archival metastatic tissue can be used if available in lieu of a biopsy if done when patient had CRPC and within 3 months

## 6.3 Cycle 1, Day 1

- Physical Examination with vital signs and weight
- ECOG Performance Status
- CBC with differential and platelet count
- Lipase (if not obtained during screening)
- CMP (with direct bilirubin with known Gilbert's syndrome)
- PSA
- LDH
- Concomitant medications
- Circulating Immune Activity sample (may be collected at screening or pre-dose C1D1)
- cfDNA (may be collected at screening or pre-dose C1D1)
- Skeletal-related events
- Adverse events
- Dispense oral study drug and compliance accounting

## 6.4 Cycle 1, Day 14

- Vital Signs
- Adverse Events

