## **10 MEASUREMENT OF EFFECT**

All baseline evaluations will be performed as closely as possible to the beginning of treatment. For subsequent evaluations, the method of assessment and techniques will be the same as those used at baseline.

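### The baseline cytokine sample may be drawn from Day -30, so for some patients it can precede the end of prior therapy, and the measured change on cabozantinib can then include the effect of stopping that therapy

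*Combined protocol and SAP*

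**What the plan says.** **Sampling window.** Footnote 4 in Section 6.1 states "cfDNA, circulating immune activity, lipase can be collected within 30 days prior to C1D1 or pre-dose C1D1". The visit lists in Sections 6.2 and 6.3 repeat the choice: "Circulating Immune Activity sample (may be collected at screening or pre-dose C1D1". Nothing requires the sample to follow the last dose of prior therapy. Footnote 8 puts the first on-treatment immune sample at Cycle 4 Day 1.

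**Prior therapy (Section 4.3).** The exclusions relevant here are:
- Exclusion 2: "Receipt of any type of small molecule kinase inhibitor (including investigational kinase inhibitor) within 2 weeks before first dose of study treatment".
- Exclusion 3: other systemic anticancer therapy, "except agents to maintain castrate status within 4 weeks before first dose of study treatment".
- Exclusion 4: "Subject has received abiraterone acetate or enzalutamide within 2 weeks before enrollment". This one counts back from enrollment, not from first dose.
- Exclusion 5: bone radiotherapy within 2 weeks of first dose, and "Systemic treatment with radionuclides within 6 weeks before the first dose of study treatment".

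**Analysis.** Section 2.5 sets out to compare interleukin-8, -6 and -1 before and on treatment, with a fall attributed to treatment as its leading hypothesis. Section 12.4 tests change from baseline with a paired t-test or signed-rank test. It does not list cytokines by name, but no other rule covers them. It has no term for prior drug or draw date.

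**General rule.** Section 10 says "All baseline evaluations will be performed as closely as possible to the beginning of treatment", with no limit in days.

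**The concern.** In a single-arm trial the patient's own baseline is the only comparator. If that baseline is drawn while the patient is still receiving an earlier treatment, the later sample differs from it in two ways: cabozantinib has been started and the earlier treatment has been stopped. A paired test cannot separate them.

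The shift could produce an apparent fall in the cytokines or hide a real one. It could also vary between sites according to when each habitually draws the tube. A baseline taken too early cannot be replaced once dosing begins.

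**Working it through.** The plan gives no sample size, power or significance level for the cytokine analysis, so there is no stated figure to reproduce. The check is arithmetic on the two windows, followed by an illustration.

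**Step 1: can a sample precede enrollment?** Yes. Section 4.6 defines screen failures as "participants who consent to participate in the clinical trial but are not subsequently randomly assigned to the study intervention or entered in the study", so consent and screening come before entry. Screening samples may be drawn from Day -30.

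**Step 2: overlap.** Largest number of days by which the sample can precede the last permitted exposure = 30 minus the washout in days before first dose.
- Kinase inhibitor (exclusion 2) or bone radiotherapy (exclusion 5): 30 - 14 = 16 days.
- Other systemic therapy (exclusion 3): 30 - 28 = 2 days.
- Radionuclides (exclusion 5): 30 - 42 = -12, so no overlap.
- Abiraterone or enzalutamide (exclusion 4): 30 - 14 - g = 16 - g, where g is the number of days from enrollment to first dose. The documents do not give g. For g = 0, 3, 7, 14 and 16 the overlap is 16, 13, 9, 2 and 0 days.
- Abiraterone or enzalutamide, if exclusion 3 is read to cover them: 2 days at most.

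**Step 3: where the on-treatment sample falls.** Cycle 4 Day 1 is 3 × 28 = 84 days, or 12 weeks, after first dose. Prior therapy has stopped by then, so an on-therapy baseline places its withdrawal inside the measured change.

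**Step 4: illustration only.** None of these inputs is in the documents. Assume 20 evaluable pairs, a within-patient change with SD 1, a fraction f of patients sampled on prior therapy, and a common shift s from stopping it. The mean bias is f × s and the SD becomes √(1 + f(1 - f)s²). For f = 0.5 and s = 0.5 the bias is 0.25 and the SD is √1.0625 = 1.031. A two-sided 5% paired t-test (noncentral t) then gives the results below. Power is for a true fall of 0.6 SD when the shift opposes it; with no bias it is 72%.

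| f | s (SD) | False-positive rate | Power |
|---|---|---|---|
| 0.10 | 0.25 | 5.1% | 68% |
| 0.25 | 0.25 | 5.8% | 62% |
| 0.25 | 0.5 | 8.1% | 50% |
| 0.25 | 1.0 | 16.4% | 28% |
| 0.50 | 0.5 | 17.8% | 30% |
| 0.50 | 1.0 | 47.6% | 7% |

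More patients do not cure a bias. With 30 pairs, f = 0.5 and s = 0.5, the false-positive rate rises from 17.8% to 25.0%.

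**Step 5: after the fix.** With the tube drawn pre-dose on Cycle 1 Day 1, the overlap is 0 days under every rule above. The sample falls at least 14 days after a kinase inhibitor, bone radiotherapy, abiraterone or enzalutamide.

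**The case against.** Several points on the other side stand.

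- **Scope.** Sixteen days is a ceiling. Chemotherapy and biologics overlap by at most 2 days and radionuclides not at all. The treatments that Section 2.1 lists for metastatic disease include no kinase inhibitor, so the full 16-day drug case may be uncommon. A pre-dose Cycle 1 Day 1 draw is already allowed, and Section 10 leans that way.
- **Size.** The illustration assumes one shift, in one direction, for very different prior treatments. With mild inputs the distortion is negligible.
- **Existing data.** Section 6.2 records dates of prior therapy, and footnote 12 records medications from 30 days before treatment. The problem could be examined without moving the sample. No such analysis is planned, however, and it would divide about 30 patients.
- **Limits of the remedy.** Disease course over 12 weeks, and any withdrawal effect lasting beyond the washout, stay mixed with the drug effect.

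A reader might infer three stronger things that the documents do not support:

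- *That steroid withdrawal is the mechanism.* Section 2.1 pairs abiraterone with prednisone, but nothing says prednisone stops with it. No general steroid washout is set, and Section 7.9 allows short courses on study.
- *That baseline cell-free DNA should also move to Cycle 1 Day 1.* Footnote 5 and Section 9 deliberately tie it to the biopsy. Keeping that link and adding a second baseline would cost an extra tube and a fourth assay run, where Section 2.5 plans three.
- *That exclusion 3 settles the abiraterone and enzalutamide case.* Read literally it could reach them, but exclusion 4 then has little left to do. The text leaves this open.

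**Conclusion.** The concern holds as a possibility for some patients. It is not a feature of every baseline, and a reader who concluded that the measured change always contains a withdrawal effect would go too far.

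What the text establishes is that the schedule accepts a cytokine baseline drawn before prior therapy ends, by up to the number of days in Step 2, and that the paired analysis has no means of allowing for it. The figure for abiraterone and enzalutamide matters most, because Section 4.1 requires progression after androgen-receptor-directed therapy. It depends on the unstated enrollment-to-dose gap and on how exclusions 3 and 4 fit together.

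The size of any bias is unknown. The documents give neither a withdrawal effect on cytokines nor the share of patients likely to be sampled early, so the error rates above show sensitivity to assumptions and are not estimates. The consequence is confined to exploratory objectives: radiographic progression-free survival, tumor response, PSA decline and overall survival are untouched. This is a cheap improvement to the plan, not a threat to its main conclusions.

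**What to change.** 1. Amend footnote 4 and Sections 6.2 and 6.3 so that the baseline circulating immune sample is drawn pre-dose on Cycle 1 Day 1. Blood is already taken then for blood count, metabolic panel, PSA and LDH, so this adds no visit and no needle stick. The cost is a text edit and the loss of an earlier backup if the tube is missed.
2. Reconcile exclusions 3 and 4, so that it is clear which interval applies to abiraterone and enzalutamide and whether it runs from enrollment or from first dose.
3. Leave cell-free DNA timing tied to the biopsy. Add to Section 12.4 a sensitivity analysis of cell-free DNA change by time since last prior dose, using the dates already recorded. This needs no new data, though it will be imprecise with 30 patients.
4. When cytokine results are reported, state that disease course to Cycle 4 Day 1 and longer-lasting withdrawal effects cannot be separated from the drug effect in a single-arm trial.
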